## 13.3.Subgroup Analyses

Subgroup analyses will be undertaken on: (i) variables used in the minimisation algorithm other than site (i.e. age); and (ii) other variables of prognostic importance to explore the effect of context, pre-specified as feeding intentions, mother's education, Index of Multiple Deprivation (IMD) and relationship status. Subgroup analyses will be limited to the primary outcome only. Tests for statistical heterogeneity (e.g. by including the treatment group by subgroup interaction parameter in the regression model) will be presented alongside the effect estimate and 95% CI within subgroups. The results of subgroup analyses will be treated with caution and will be used for the purposes of hypothesis generation only.

## 13.4. Missing Data and Sensitivity Analyses

Every attempt will be made to collect full follow-up data on all study participants, it is thus anticipated that missing data will be minimal. Participants with missing primary outcome data will not be included in the primary analysis in the first instance. This presents a risk of bias, and sensitivity analyses will be undertaken to assess the possible impact of the risk. In brief, this will include an assumption in which those with missing data will be assumed to not be breastfeeding; in the ABA feasibility study, most women who did not respond to the follow-up questionnaire were formula feeding. Further sensitivity analyses will be considered to explore fidelity of delivery e.g. Complier Average Causal Effects analysis.

Full details will be included in the SAP.

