# 8.2. Main Trial Outcomes

#### 8.2.1. Primary Outcome

Any breastfeeding at 8-weeks post birth, defined in accordance with the UK Infant Feeding Survey 'as infant being breastfed (including being given expressed breastmilk), within the past 24 hours, even if they are also receiving infant formula, solid food or other liquids'.

This will be measured by self-report in the 8-week questionnaire (or subsequent text message for non-responders), with missing data supplemented from health visitor records (women report their feeding method to their health visitor at the 6-8 week check as part of the Healthy Child Programme in England, Healthy Child Wales Programme and Child Health Surveillance Programme in Scotland which provide routine data to varying levels of completeness).

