### 8.2.2.1. Clinical

- Breastfeeding initiation defined as baby put to the breast, even if this was on one occasion only and includes giving babies expressed breast milk.
- $\circ$   $\,$  Any breastfeeding at 16-weeks post birth.
- Any breastfeeding at 24-weeks post birth.
- Exclusive breastfeeding at 16-weeks post birth (defined in accordance with the WHO definition of infants who received only breast milk during the previous 24 hours);
   "Exclusive breastfeeding is defined as the baby receiving no other food or drink, not even water, except breast milk (including milk expressed), but allows the infant to receive oral rehydration solution, drops and syrups (vitamins, minerals and medicines)."
- Exclusive breastfeeding at 24-weeks post birth.
- Time to cease exclusive feeding with breastmilk, up to 16-weeks.
- $\circ$  Time to cease feeding with any breastmilk, up to 16-weeks.
- Maternal anxiety at 8-weeks post birth (measured by the Generalised Anxiety Disorder Assessment (GAD-7))
- Maternal anxiety at 16-weeks post birth (measured by the GAD-7)
- Maternal health related quality of life at 8-weeks (measured by the EuroQol (EQ-5D-5L))
- Maternal health related quality of life at 16-weeks (measured by the EQ-5D-5L)
- Maternal social support at 8-weeks post birth (measured by Medical Outcomes Study (MOS) Emotional / Informational Support domain;)
- Maternal social support at 16-weeks post birth (measured by MOS Emotional / Informational Support domain;)
- The following maternal self-reported formula feeding practices (how formula is prepared) (using questions from the UK Infant Feeding Survey;) at 8-weeks post birth and 16-weeks post birth:
  - Making one feed at a time
  - Correct water temperature

- Adding formula powder before water
- $\circ$  Making up formula when needed when out of the home
- Keeping milk chilled when out of the home
- Making formula with hot water when out of the home
- Sterilising bottles using recommended methods
- Maternal use of support for infant feeding (e.g. national breastfeeding helpline; peer support; breastfeeding groups) at 8-weeks post birth and 16-weeks post birth.
- Diagnosis of tongue tie in baby and whether treated, measured at 8-weeks post birth.

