# **13. STATISTICAL CONSIDERATIONS**

## 13.1. Sample Size

Assuming 90% power and a 2-sided 5% significance level, with a control group rate of 44% for the primary outcome (95% CI 30.0% to 58.7%; from the ABA feasibility data), a sample size of 2,136 women (1,068 per group) would be required to detect a risk ratio of 1.16 (i.e. an increase of 7% from 44% to 51%), considered to be a clinically meaningful increase. Since the intervention will be delivered by IFHs, there is a potential for clustering of outcomes by IFH. To allow for this potential clustering effect the sample size for the intervention arm requires inflation, assuming an intra-cluster correlation coefficient of 0.039 taken from ABA feasibility data and given that each IFH will support about 12 women. The sample size required for the intervention arm is thus 1,526, giving a total sample size of 2,594 (1526 intervention + 1068 control). Allowing for a 5% loss to follow-up (as in the ABA feasibility study), a total of 2,730 (1,606 intervention and 1,124 control arm) women would be required (2594/0.95).

Assuming 80% power, the sample size of 2,730 would allow the detection of a risk ratio of 1.14 equivalent to a 6% absolute increase.

With an average 12 women/IFH we need to train 134 peer supporters (1606/12).

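### Women with no 8-week feeding status are dropped before the stopping time and the 16- and 24-week answers, which would settle some of them, are consulted

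*Protocol*

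**What the plan says.** Protocol 8.2.1 defines the primary outcome as any breastfeeding in the previous 24 hours at 8 weeks. It fixes the sources in order: the 8-week questionnaire, a text message to non-responders, and then routine records ("with missing data supplemented from health visitor records"). Section 10.4 repeats the text and routine-data steps. Section 8.2.1 also says that the completeness of the routine data varies.

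For women still without a value, section 13.4 says: "Participants with missing primary outcome data will not be included in the primary analysis in the first instance". It calls this a risk of bias and reports that in the feasibility study "most women who did not respond to the follow-up questionnaire were formula feeding". It names one check, in which "those with missing data will be assumed to not be breastfeeding". It presents this as a summary and leaves full details to the SAP.

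Section 8.2.2.1 lists as secondary outcomes "Time to cease feeding with any breastmilk, up to 16-weeks" and any breastfeeding at 16 and 24 weeks. Section 8.3.2 sends the 16- and 24-week questionnaires to the women in follow-up and does not make them conditional on an 8-week reply. Section 13.6 places the final analysis after the 24-week assessment.

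**The concern.** A woman who misses every 8-week source may still answer at 16 weeks. If she then reports that she stopped at five weeks, or that she is still breastfeeding, her 8-week status is known for practical purposes. Under 8.2.1 and 13.4 as written she counts as missing and leaves the primary analysis. The same answer makes her an event, or a woman still breastfeeding, in the secondary analysis of time to stopping. The dataset would then hold her status for one outcome and treat it as unknown for the more important one.

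What is at stake is bias rather than power. The trial is open (6.5) and only the intervention arm has repeated helper contact (7.1.2), so unequal loss between arms is plausible, although the protocol does not predict it. If loss is unequal and related to feeding, the complete-case estimate moves. Each value derived from data in hand makes the result depend less on assumptions about missing women.

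**Working it through.** **1. The plan's own figures (13.1).** The inputs are stated there: "Assuming 90% power and a 2-sided 5% significance level, with a control group rate of 44% for the primary outcome", 51% in the intervention arm, and clustering in the intervention arm only, "assuming an intra-cluster correlation coefficient of 0.039 taken from ABA feasibility data", with about 12 women per helper.
- Pooled two-proportion formula: n = [1.960·√(2·0.475·0.525) + 1.282·√(0.44·0.56 + 0.51·0.49)]² / 0.07² = 1,068 per group after rounding up.
- Design effect: 1 + 11·0.039 = 1.429. Intervention arm: 1,068·1.429 = 1,526. Total: 1,526 + 1,068 = 2,594.
- Allowing for 5% loss: 1,526/0.95 = 1,606 and 1,068/0.95 = 1,124, total 2,730.

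The sample size reproduces. The planned loss is 0.05·2,730, or about 137 women. With nobody missing, power is 91.4%; with 5% lost it is 90.0%. Recovering values therefore adds little power.

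**2. What each further item settles.**

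| Later answer | 8-week status |
|---|---|
| Never started | No |
| Stopped before 8 weeks | No |
| Stopped after 8 weeks | Yes |
| Still breastfeeding at 16 or 24 weeks | Yes, barring a pause and restart |
| Not breastfeeding at 16 or 24 weeks, no stopping time | Not settled |

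The protocol does not say how many women miss all three 8-week sources yet answer later, so the yield is unknown.

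**3. Illustrative size of the bias.** The following are assumptions, not protocol figures: no effect (44% in both arms), a share m missing in each arm, and a breastfeeding rate r among missing women that is the same in both arms.
- Complete case, per arm: (0.44 - r·m)/(1 - m).
- Missing counted as not breastfeeding, per arm: 0.44 - r·m.
- SE of the difference: √[0.44·0.56·(1.429/1,526 + 1/1,068)] = 0.0215.
- Two-sided rejection rate: P(|Z + bias/SE| > 1.96).

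With 3% missing in the intervention arm and 7% in control (about 4.6% overall):
- Complete case, r = 0: 0.44/0.97 - 0.44/0.93 = 0.4536 - 0.4731 = -1.95 points; rejection 14.9% against a nominal 5%.
- Complete case, r = 0.20: 0.434/0.97 - 0.426/0.93 = -1.06 points; rejection 7.9%.
- Missing as not breastfeeding, r = 0.44: 0.4268 - 0.4092 = +1.76 points; rejection 13.0%.

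With 4% and 6% missing, the first and third become about -1.0 and +0.9 points, with rejection about 7%. With 5% in each arm both are zero. Swapping the arms reverses the signs.

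**4. What recovery could buy.** Take true rates of 44% and 51%, r = 0, and 6.4% of the intervention arm and 3% of the control arm missing (5% overall). The complete-case difference is 0.51/0.936 - 0.44/0.97 = 9.13 points, or 2.1 too high. If half the missing values in each arm were derived (about 137 women down to 68), it is 0.51/0.968 - 0.44/0.985 = 8.02 points, or 1.0 too high. The one-half is an assumption.

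**The case against.** The strongest objection is that handling of missing data belongs in the SAP. Section 13.4 says so, admits the risk of bias, and does not present its list of checks as complete. That stands for sensitivity analyses. A reader might infer that no imputation or tipping-point analysis is planned, but the protocol cannot show this. It does not dispose of the derivation step, because 8.2.1 itself fixes where the primary outcome comes from.

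Three other stronger readings are tempting and are not supported.
- **That the protocol shows the dropped women are mostly formula feeding.** The feasibility remark concerns questionnaire non-responders. Here many of them may be filled in by text or health visitor record, and some who stop follow-up can still allow routine data for the primary outcome (8.4). Nothing describes the women left after all three sources.
- **That many values can be recovered.** No count is given, and women missed three times at 8 weeks may also be missed later.
- **That the primary result will be biased.** This needs unequal loss by arm, which is assumed above. With equal 5% loss the risk ratio barely moves: with true rates of 44% and 51% it stays at 1.159 if no missing woman breastfeeds. If missing women breastfeed at a common rate between 0 and the responders' rate, the no-effect illustration puts the two planned analyses on either side of the truth. In the 3% and 7% case nearly all of the 14.9% falls against the intervention; false rejection in its favour is about 0.2%.

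It is also fair to say that a recalled stopping time is not the 24-hour measure used for responders. That is a real but small cost. Responders' own answers already span 14 days before to 30 days after week 8 (the assessment schedule in 8.3.2), so the planned measure is not tied exactly to day 56 either.

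**Conclusion.** The point holds as an inexpensive improvement to the definition of the primary outcome. The source list in 8.2.1 stops short of data the trial collects anyway, and 13.4 then excludes women whose 8-week status some of those data would settle. This follows from the text alone.

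The size is not known. The illustration of about -2 points (complete case) and +1.8 points (missing as not breastfeeding), against a 7-point target, rests on an assumed 3% and 7% loss, 44% in both arms, and extreme assumptions about the missing women. Both figures are zero with equal loss and no effect. The numbers show why derivation is worth a sentence in the plan; they do not show that the planned analysis is wrong. An arm-specific tipping-point analysis is something to confirm in the SAP, and its absence from the protocol is not an error.

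**What to change.** In 8.2.1, with a cross-reference in 13.4, add a last step before a woman counts as missing, applied identically in both arms:
- reported stopping before 8 weeks, or never having started: not breastfeeding at 8 weeks;
- reported stopping after 8 weeks, or still breastfeeding at 16 or 24 weeks: breastfeeding at 8 weeks;
- otherwise: missing, handled as 13.4 already says.

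Report the number of derived values by arm, and repeat the primary analysis without them. Separately, confirm in the SAP whether the assumed rate among the remaining missing women will be varied by arm.

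The cost is wording and a little programming. No new data are needed, and there is no delay because the final analysis already waits for week 24. The downside is reliance on short recall, and on a measure slightly different from the 24-hour definition, for a few women; the repeat analysis shows whether that matters.

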## 13.2.1. Primary Outcome

The primary outcome (i.e. baby receiving any breast milk' at 8-weeks post birth) is a binary outcome (i.e. yes/no) and will be analysed using a mixed effects log binomial regression model, adjusting for the intervention group and the minimisation variables listed in Section 6.2 (age group and site). Age (as a continuous variable) will be treated as a fixed effect and site and IFH will be treated as random effects. The treatment effect will be expressed as an

adjusted risk ratio and a risk difference with associated 95% CIs. If the model does not converge, alternative models will be considered, e.g. log Poisson regression models with robust variance estimation. The p-value from the associated model will be produced and used to determine statistical significance of the estimated treatment group parameter.

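### The one missing-data check named for the primary outcome gives missing women the same value in both arms, so it cannot show what happens if their feeding differs by arm

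*Protocol*

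**What the plan says.** Protocol section 13.4 leaves women with a missing primary outcome out of the primary analysis in the first instance. On that choice it says: "This presents a risk of bias, and sensitivity analyses will be undertaken to assess the possible impact of the risk". It then outlines the check: "In brief, this will include an assumption in which those with missing data will be assumed to not be breastfeeding". The reason given is that most non-responders in the feasibility study were formula feeding; no percentage and no split by arm is given. Full details are left to the SAP.

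The other sensitivity analyses named answer different questions. The complier average causal effect analysis (13.4) is for fidelity of delivery, and the per-protocol analysis (13.2) is for adherence.

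Section 13.2.1 reports the primary effect as an "adjusted risk ratio and a risk difference with associated 95% CIs". Section 13.1 allows one overall loss of 5% and gives no rate by arm. Section 8.2.1 takes the outcome from the woman's own report by questionnaire or text, with gaps filled from health visitor records of varying completeness. Section 6.5 states that the trial is unblinded.

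**The concern.** The bias that matters for a comparison between arms is that women with missing outcomes feed differently in the two arms. That is plausible here. Participants know their allocation, the outcome is self-reported, and intervention women have a continuing relationship with a feeding helper that could affect who answers. For example, intervention women who have stopped breastfeeding might be less willing to reply than control women who have stopped.

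A rule that gives every missing woman the same value never varies this. If loss is similar in the two arms, the RR after imputation will match the complete-case RR by construction. That agreement could then be reported as robustness to missing data when, on the RR scale, it carries no information about the question.

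**Working it through.** **Inputs from section 13.1.** Control rate 44%; target 51% (RR 51/44 = 1.159, RD 7 points); 90% power, two-sided 5%; intra-cluster correlation 0.039 with about 12 women per helper, intervention arm only; 5% loss; 1,606 intervention and 1,124 control.

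**Assumptions made here.** Loss by arm, breastfeeding rates among missing women, and an observed result of 49% v 44%. The protocol gives none of these.

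**The plan's own figures reproduce.** Two proportions, pooled variance, no continuity correction: 1,068 per group, matching "a sample size of 2,136 women (1,068 per group) would be required". Design effect 1 + 11 × 0.039 = 1.429; 1,068 × 1.429 = 1,526. After loss: 1,526/0.95 = 1,606 and 1,068/0.95 = 1,124.

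**Algebra.** Let p be the rate among responders, m the share missing and q the breastfeeding rate among the missing. An arm's rate is p(1 − m) + qm. The named check sets q = 0 in both arms, so

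RR = [p1(1 − m1)] / [p0(1 − m0)].

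If m1 = m0, the loss terms cancel and the RR is the complete-case RR. If not, it is multiplied by (1 − m1)/(1 − m0), which depends on response rates alone. This is exact for the crude RR; the adjusted RR could shift slightly if missingness varies by site or age.

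**The named check at equal loss, 51% v 44% among responders**

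| Missing in each arm | RR | RD (points) |
|---|---|---|
| Complete case | 1.159 | 7.0 |
| 5% | 1.159 | 6.65 |
| 10% | 1.159 | 6.3 |
| 20% | 1.159 | 5.6 |

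**The named check at unequal loss, same responder rates.** Intervention 10% / control 5% missing: RR 1.159 × 0.90/0.95 = 1.10. Intervention 5% / control 10%: RR 1.159 × 0.95/0.90 = 1.22.

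**Values that differ by arm, design effect (51% v 44%).** RR with 95% CI on the log scale, variance × 1.429 in the intervention arm:

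| Loss per arm | q intervention | q control | RR (95% CI) |
|---|---|---|---|
| 5% | 0 | 0 (named check) | 1.16 (1.06 to 1.27) |
| 5% | 25% | 44% | 1.13 (1.03 to 1.23) |
| 5% | 0 | 44% | 1.10 (1.01 to 1.20) |
| 10% | 0 | 44% | 1.04 (0.95 to 1.14) |

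**A smaller significant result (assumed 49% v 44%), 5% loss per arm.** Wald test of the RD with the same design effect; 1,526 and 1,068 women for complete case, 1,606 and 1,124 otherwise:

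| Analysis | Rates compared | RR | RD (points) | p |
|---|---|---|---|---|
| Complete case | 49.0% v 44.0% | 1.114 | 5.0 | 0.020 |
| Named check (0 / 0) | 46.55% v 41.8% | 1.114 | 4.75 | 0.023 |
| q = 0 / 22% | 46.55% v 42.9% | 1.085 | 3.65 | 0.08 |
| q = 0 / 44% | 46.55% v 44.0% | 1.058 | 2.55 | 0.22 |

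For example, in the last row the control rate is 0.44 × 0.95 + 0.44 × 0.05 = 44.0%, and the intervention rate is 0.49 × 0.95 = 46.55%.

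**The case against.** Several points on the other side stand.

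- **The outline is not exhaustive.** A reader might infer that no other missing-data analysis is planned. The text does not support that: it speaks of sensitivity analyses in the plural, says what they will include, and defers full details to the SAP, which is not at hand. One can say only that no other check on missing outcomes is named.
- **The check is not empty.** A reader might infer that it cannot test for bias at all. It can show some: the RR moves when loss differs by arm (1.10 to 1.22 above), and the RD, also a reported measure, moves even at equal loss. Equal loss is a condition set in the working; section 13.1 does not state it. If intervention women who stopped breastfeeding go missing more often, zero is the right value for them and the check does lower the RR.
- **It does not systematically inflate the effect.** A reader might infer this from cases where controls lose more women. Take loss of 3% v 8% (5.1% overall) with 44% breastfeeding among responders in both arms. The check gives RR 0.97/0.92 = 1.054 and RD +2.2 points, p = 0.29. If 20% of missing women in fact breastfeed, the true RD is +1.2. The check is then 1.0 point off and complete case (RD 0) is 1.2 points off, so the check is the nearer of the two.
- **Recovery of outcomes is planned.** An outcome is missing only after the questionnaire, a text to non-responders and a search of health visitor records (8.2.1, 10.4). Those records do not depend on the woman answering the trial, although their completeness varies.
- **The change in p depends on the chosen result.** It uses 49% v 44%; at the design effect and 5% loss the conclusion holds. No figure in the protocol supports a particular difference between arms among missing women.

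What remains is that the one scenario the protocol commits to uses a common value, so it cannot represent a difference between arms in missing women's feeding.

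**Conclusion.** The point holds as an inexpensive improvement to a stated method; it is not an error that invalidates the plan. Counting missing women as not breastfeeding is a plausible scenario with an empirical reason behind it. As the only named check on a bias the protocol itself acknowledges, it says little on the RR scale: at equal loss the crude RR is fixed, and at unequal loss it follows response rates alone.

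The size depends on the result. With 5% loss per arm and the full design effect, the conclusion survives the 0% intervention / 44% control corner (RR 1.10, lower limit 1.01). With an assumed 49% v 44% it does not: p goes from 0.02 to 0.08 when 22% of missing controls breastfeed, and to 0.22 when 44% do. With 10% loss the design effect does not survive that corner either (RR 1.04, 0.95 to 1.14). These figures rest on crude comparisons, equal loss, a design effect of 1.429 in the intervention arm only, and assumed rates among missing women.

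**What to change.** In section 13.4, keep the analysis that counts missing women as not breastfeeding as one scenario. Add a sentence, with detail in the SAP, that the breastfeeding proportion among women with missing outcomes will be varied separately in each arm, from 0% to that arm's observed rate. The grid should include the corner of 0% in the intervention arm and the observed control rate in the control arm. Report the RR and RD with 95% CIs across the grid, and state where the conclusion changes. Settle this before outcome data by arm are examined, since section 6.5 allows the trial statisticians to be unblinded.

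The cost is a few more model runs and one table or figure, with no new data. The downside is that a positive result may look less robust than under the single scenario.
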